5.3 Secondary Safety Estimand

Secondary Objective 2.3.2.1: To explore the safety of mRNA-based COVID-19 vaccines among participants with prior COVID-19 who received investigational therapy or its comparator for COVID-19 and persons who are SARS-CoV-2 naïve.
	
Estimand description	Occurrence of adverse events up to 56 and 140 days after receiving the first dose of an mRNA-based COVID-19 vaccine among individuals receiving at least one dose of the vaccine with and without prior history of COVID-19.
Treatment	
Cohort 1a: Moderna mRNA-1273 COVID-19 vaccine, 100 µg (0.5 mL) to be administered intramuscularly (IM) at Entry and Day 28. Both doses will be provided by the study.
 
Or
 
Cohort 1b: Participants will receive a two-dose series of a community-provided mRNA-based COVID-19 vaccine that has received FDA EUA or FDA approval (e.g., Moderna or Pfizer). Vaccine will not be provided by the study.
 
NOTE: These participants may enter the study before their first vaccine dose, after their first vaccine dose, or after their second vaccine dose.
 
Or
 
Cohort 1c: Participants will receive their first Moderna mRNA-1273 COVID-19 vaccine dose in the community. Their second Moderna mRNA-1273 dose will be provided by the study (100 µg [0.5 mL] to be administered IM 28 days after their first dose).
 
Or
 
Cohort 2: Participants will receive the following study-provided regimen: Moderna mRNA-1273 COVID-19 vaccine, 100 µg (0.5 mL) to be administered IM at Entry and Day 28.

Target population	Analysis sets
Individuals who received an mRNA-based COVID-19 vaccine with and without a prior history of COVID-19.	Safety Set (all enrolled participants who received at least one dose of vaccine)
Variable	Outcome measures
Occurrence of an adverse event up to 56 and 140 days after first dose of an mRNA-based COVID-19 vaccine.	
New Grade 3 or higher AE, SAE, or AE leading to change or discontinuation in vaccine receipt from first dose of the mRNA-based COVID-19 vaccine and through 140 days after the first dose of the vaccine.
 
Grade 1 or higher allergic reaction from first dose of the mRNA-based COVID-19 vaccine through the visit 56 days after the first dose of the vaccine.
 
Grade 2 or higher injection site reaction from first dose of the mRNA-based COVID-19 vaccine through the visit 56 days after the first dose of the vaccine.

Handling of intercurrent events	Handling of missing data


The following intercurrent events are relevant to the estimand:
 
 1. Reinfection with SARS-CoV-2 between first and second vaccine doses. Post vaccination observations through the respective time point of interest (56 or 140 days) after first vaccine dose will be used to determine the variable (treatment policy strategy) 2. Discontinuation of treatment after first vaccine dose due to safety event(s). All observations through the respective time point of interest (56 or 140 days) after first vaccine dose will be used to determine the variable (treatment policy strategy) 3. Discontinuation of treatment after first dose of vaccine due to non-safety reasons. All observations through the respective time point of interest (56 or 140 days) after first vaccine dose will be used to determine the variable (treatment policy strategy) 4. Death prohibiting subsequent existence of the variable. Observations before death will be used to determine the variable (while alive strategy) 	
Participants who discontinue follow-up before the respective time point of interest (56 or 140 days) after the first dose of the vaccine will have their outcome measures determined based on data available until the time of study discontinuation. This implicitly assumes that the participants would not have had an applicable AE had they been observed to the time point of interest.
 
Sensitivity analyses:
 
We will consider those participants who discontinued follow-up before the time point of interest (56 or 140 days) after the first vaccine dose as having at least one adverse event.
 
We will only include participants who were not re-infected with SARS-CoV-2 between first and second doses of the vaccine.


Population-level summary measure
 
Probability of having at least one Grade 3 or higher adverse event following first dose of vaccine through 140 days after the first vaccine dose.
 
Probability of having a Grade 1 or higher allergic reaction from the first dose of vaccine through 56 days after the first vaccine dose.
 
Probability of having a Grade 2 or higher injection site reaction from first dose of vaccine through 56 days after the first vaccine dose.
	
Analysis approach
 
Proportions and confidence intervals described below will be estimated for:
 
 (1) Participants exposed to AZD7442 IM or IV, BRII-196+BRII 198 IV, SAB 185 (3,840 or 10,240 units/kg), BMS 096414+BMS 986413 subcutaneous or Camostat in ACTIV-2/A5401 (2) Participants exposed to placebo in ACTIV-2/A5401 (3) Participants without prior history of COVID-19 
(note that for the safety analysis, Camostat is considered an active agent)
 
Proportion of participants with at least one Grade 3 or higher adverse event through 140 days after the first vaccine dose and exact 95% confidence interval.
 
Proportion of participants with a Grade 1 or higher allergic reaction from the first dose of vaccine through 56 days after the first vaccine dose and exact 95% confidence interval.
 
Proportion of participants with a Grade 2 or higher injection site reaction from first dose of

	vaccine through 56 days after the first vaccine dose and exact 95% confidence interval.
--	---

Supplemental Analyses

If sample size permits, analyses will be carried out in subgroups defined by levels of sex and levels of race/ethnicity.

6 Analysis of other secondary objectives

6.1.1 Relative pre-vaccine to post-vaccine change in NAb response defined as the ratio of post-vaccine level/pre-vaccine level by received vaccine, i.e., Moderna versus Pfizer. The pre-vaccine NAb measurement will be obtained before the first dose of the vaccine, and the post-vaccine measurement will be obtained at least 56 days after the first dose of the vaccine. (Objective 2.3.1.1)

This outcome measure will follow the Key Secondary Estimand analysis outlined in Section 5.2. We will report the relative change in geometric mean NAb levels among those who received the Moderna vaccine versus the Pfizer vaccine. We will report the ratio of change in geometric mean neutralizing antibody levels comparing those who received Moderna to Pfizer from before first vaccine dose to Day 56 study visit, together with the corresponding 95% confidence interval.

7 Report Contents

All tables, listings, and figures provided in the final report will include totals and summary statistics overall and by select investigational therapy group from ACTIV-2/A5401 (by receipt of active therapy, placebo, or among the 3 groups listed in Section 2.4).

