Participants will receive their first Moderna mRNA-1273 COVID-19 vaccine dose in the community. Their second Moderna mRNA-1273 dose will be provided by the study (100 µg [0.5 mL] to be administered IM 28 days after their first dose).

NOTE: These participants may enter the study before or after their first vaccine dose.

Participants without prior history of SARS-CoV-2 infection

Participants will receive the following study-provided regimen: Moderna mRNA-1273 COVID-19 vaccine, 100 µg (0.5 mL) to be administered IM at Entry and Day 28.

c. Section 3.0 Study Design

The last sentence of the second paragraph: “Participants will have blood collected and immune responses measured before the first vaccine dose (if feasible), and before the second dose of vaccine (e.g., 28 days later for Moderna vaccine and 21 days later for Pfizer vaccine if given in the community) (**if feasible**), and 56 (**if feasible**), 140, 365, and 730 days after **their first vaccine dose** (Figure 3.0-1).”

d. Section 4.2 Exclusion Criterion 4.2.2

This criterion was revised as follows: “For participants who are in, or who have completed, the ACTIV-2/A5401 trial: Self-report of receipt of the ~~second~~ **first** dose of an mRNA-based COVID-19 vaccine **140 days or more before A5404 enrollment.**”

e. Section 5.1.1 Regimen and Duration

Participants will receive the following study-provided regimen: Moderna mRNA-1273 COVID-19 vaccine, 100 µg (0.5 mL) to be administered intramuscularly (IM) at **Entry** and Day 28.

Or

Participants will receive a two-dose series of a community-provided mRNA-based COVID-19 vaccine that has received FDA EUA or FDA approval.

NOTE: Participants who receive a community-provided mRNA-based COVID-19 vaccine may receive their **first and second** COVID-19 vaccine dose(s) before study entry.

Or

Participants will receive (or have recently received) a community-provided Moderna mRNA-1273 COVID-19 vaccine at (or before) **Entry** and study-provided Moderna mRNA-1273 COVID-19 vaccine, 100 µg (0.5 mL) to be administered intramuscularly (IM) at at least 28 days apart.

f. Section 6.1, Table 6.1-3

The title of this section was changed to, “~~Community Provided mRNA-based COVID-19 Vaccine~~ Schedule of Evaluations for ACTIV-2/A5401 Participants **who Received First Dose of a Community-Provided mRNA-based COVID-19 Vaccine Before Entry or Will Receive First Dose After Entry**”

g. Section 6.1, Table 6.1-4 was added:

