56 and 140 Days Post-Vaccination #1 for ACTIV-2/A5401 Participants Who Received First and Second Doses of a Community-Provided mRNA-based COVID-19 Vaccine before Entry

- **56 days post-vaccination #1 timepoint:**
 - This visit will not be conducted if the participant enrolls more than 56 days after their first vaccine dose.
 - This visit may be combined with the Entry visit if the participant enrolls between 56 and 63 days after their first mRNA COVID-19 vaccine dose. Evaluations indicated at both timepoints will be conducted only once.
- **140 days post-vaccination #1 timepoint:** This visit may be combined with the Entry visit if the participant enrolls between 133 and 147 days after their first mRNA COVID-19 vaccine dose. Evaluations indicated at both timepoints will be conducted only once.

k. Section 6.3.7 Vaccine Administration

The first sub-section title was changed to, “Documentation of Community-Provided COVID-19 Vaccination”

l. Section 6.3.8 Vaccine Symptom Screen

The first sentence has been revised to, “For participants who receive community-provided mRNA-based COVID-19 vaccine: If the participant enrolls >14 days after the first or second dose of their vaccine, then a Vaccine Symptom Screen is not collected for the doses provided prior to enrollment.”

4. Section 4.1, Inclusion Criterion 4.1.3:

The following note was added.

NOTES:

- Selected investigational therapies will be posted on the A5404 PSWP.
- **For participants who received camostat or the active comparator/placebo for camostat: Receipt of ≥50% of the doses indicated in ACTIV-2/A5401.**

5. Section 5.2, Study Product Formulation and Preparation**a. In section 5.2.1 Formulation and Storage, the following modifications have been made:**

The Moderna mRNA-1273 COVID-19 vaccine is supplied as a frozen suspension, stored between ~~-25-50°~~ to -15°C, in multi-dose vials, and does not contain a preservative. ~~Store in the original carton to p~~ **Protect** from light. Do not store on dry ice or below ~~-40-50°C~~. The Moderna mRNA-1273 COVID-19 vaccine is white to off-white suspension. It may contain white or translucent product-related particulates.

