3.2 Secondary Outcome Measures

- 3.2.1** Relative pre-vaccine to post-vaccine change in NAb response defined as the ratio of post-vaccine level/pre-vaccine level. The pre-vaccine NAb measurement will be obtained before the first dose of the vaccine and the post-vaccine measurement will be obtained at least 56 days after the first dose of the vaccine. (Objective 2.3.1.1)
- 3.2.2** New Grade 3 or higher AE, or SAE, or AE leading to change or discontinuation in vaccine receipt from first dose of the mRNA-based COVID-19 vaccine and through 140 days after the first dose of vaccine. (Objective 2.3.2.1)
- 3.2.3** Grade 1 or higher allergic reaction from first dose of the mRNA-based COVID-19 vaccine through the visit 56 days after the first dose of the vaccine. (Objective 2.3.2.1)
- 3.2.4** Grade 2 or higher injection site reaction from first dose of the mRNA-based COVID-19 vaccine through the visit 56 days after the first dose of the vaccine. (Objective 2.3.2.1)
- 3.2.5** Relative pre-vaccine to post-vaccine change in NAb response defined as the ratio of post-vaccine level/pre-vaccine level by received vaccine, i.e., Moderna versus Pfizer. The pre-vaccine NAb measurement will be obtained before the first dose of the vaccine, and the post-vaccine measurement will be obtained at least 56 days after the first dose of the vaccine. (Objective 2.3.1.1)

4 General Considerations

The aim of this study is to describe immunologic responses to mRNA-based SARS-CoV-2 vaccine among individuals who previously received investigational therapy in ACTIV-2/A5401 for SARS-CoV-2 infection in comparison to individuals who received a placebo. As ACTIV-2/A5401 is expected to change from using a placebo control to an active control, this study's aim will also evolve to describe immunologic responses to mRNA-based SARS-CoV-2 vaccine among individuals who previously received investigational therapy in ACTIV-2/A5401 for SARS-CoV-2 infection in comparison to individuals who received an active control.

Estimates and confidence intervals for NAb will be obtained by using a log base 10 transformation on the PSV values, then using linear regression with an indicator variable for prior select COVID-19 therapy exposure versus placebo using standard methods, assuming that the \log_{10} NAb responses are approximately normally distributed within exposure group.

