7.9 Secondary Safety Estimand

- Probability of having at least one Grade 3 or higher adverse event through 140 days after the first vaccine dose.
- Probability of having a Grade 1 or higher allergic reaction from the first dose of vaccine through 56 days after the first vaccine dose.
- Probability of having a Grade 2 or higher injection site reaction from first dose of vaccine through 56 days after the first vaccine dose.
- Sensitivity analysis considering those participants who discontinued follow-up before 56 days/140 days (respective to each outcome measure) after the first vaccine dose as having at least one adverse event.
- Sensitivity analysis only among participants who were not re-infected with SARS-CoV-2 between first and second doses of the vaccine.

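### The Day 56 allergic and injection-site reaction proportions use every vaccinated participant as denominator, with no rule for late entrants whose doses were not screened for symptoms

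*SAP*

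**What the plan says.** **Outcome and denominator.** SAP 3.2 defines outcome 3.2.4, for reactions of at least Grade 2, as an "injection site reaction from first dose of the mRNA-based COVID-19 vaccine through the visit 56 days after the first dose of the vaccine"; outcome 3.2.3 has the same window for Grade 1 or higher allergic reactions. SAP 5.3 reports, for example, the "Proportion of participants with a Grade 1 or higher allergic reaction from the first dose of vaccine" through Day 56 with an exact 95% interval. It does so separately for the active-therapy, placebo and SARS-CoV-2-naive groups. The analysis set is the "Safety Set (all enrolled participants who received at least one dose of vaccine"; SAP 4.1.2 agrees, and neither section sets a condition on entry time.

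**Late entry.** The treatment row of SAP 5.3 allows Cohort 1b to enter before, between or after the two community doses. Cohort 1c may enter after its community first dose. As amended by Letter of Amendment #1 (item 3d), exclusion criterion 4.2.2 bars only a first dose received "140 days or more before A5404 enrollment".

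**What is collected.** Under item 3l (Protocol 6.3.8), if enrollment is more than 14 days after a community dose, "then a Vaccine Symptom Screen is not collected for the doses provided prior to enrollment". Under item 3j (Protocol 6.2.3), for those with both doses before entry, the Day 56 visit has this limit: "This visit will not be conducted if the participant enrolls more than 56 days after their first vaccine dose". The one exception is that it may be merged with Entry on Days 56 to 63.

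**Missing data.** The rule in SAP 5.3 is about "Participants who discontinue follow-up before the respective time point of interest (56 or 140 days) after the first dose of the vaccine". The report list in SAP 7.9 matches it: "Sensitivity analysis considering those participants who discontinued follow-up before 56 days/140 days (respective to each outcome measure") as having had an event.

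**The concern.** The missing-data rule deals with observation that stops too soon. A late entrant has the opposite problem: observation starts too late, after some or all of the reaction window has passed. The SAP does not say how such a person enters these two proportions. Taken as written, the person is in the denominator and, with no reaction on record, is counted as not having had one.

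SAP 5.2 shows that the issue was seen elsewhere. It excludes anyone vaccinated before entry from the pre-to-post antibody ratio, because the pre-vaccine sample is missing. SAP 5.3 has no counterpart. SAP 7.6 adds an inconsistency: it lists *post-entry* reactions while keeping a window that opens at first dose, whereas 5.3 and 7.9 say only from first dose. For a late entrant the two readings can give different counts.

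At stake are reaction rates, and upper limits on allergic reactions, that look more reassuring than the data allow. Only the ACTIV-2/A5401 groups can be affected. Cohort 2 receives both doses on study, so the screen waiver does not reach it.

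**Working it through.** The documents give no sample size, event rate or precision for the safety proportions, so there is no figure of the plan to reproduce. The check has two parts: which entry dates lose which data, and how far a proportion could move.

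**1. Entry windows.** Inputs: doses 28 days apart (Moderna) or 21 days (Pfizer), from SAP 2.1; the 14-day screen limit (Protocol 6.3.8), read dose by dose; last permitted entry on Day 140 − 1 = Day 139 after dose 1 (criterion 4.2.2). The dose 2 screen is lost after Day 28 + 14 = 42, or Day 21 + 14 = 35.

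| Entry, days after dose 1 | Dose 2 on Day 28 | Dose 2 on Day 21 |
|---|---|---|
| up to 14 | both screened | both screened |
| 15–35 | dose 2 only | dose 2 only |
| 36–42 | dose 2 only | neither |
| 43–139 | neither | neither |

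Cohort 1c, with a study dose 2 on Day 28, loses only the dose 1 screen, when entry is on Days 15 to 28. For entry on Days 64 to 139 no Day 56 visit is held and the whole outcome window closes before entry. These are permitted windows, not counts of participants.

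**2. Size of the shift.** Let p be the true probability of a reaction by Day 56 and p2 the probability of one after dose 2. Let f0 be the share of a group screened for neither dose and f1 the share screened for dose 2 only. With no other source of data and unscreened time counted as event-free:

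expected reported rate = p − f0·p − f1·(p − p2)

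The simpler form p(1 − f), with f = f0 + f1, is the extreme case. It overstates the loss when f1 > 0, because dose 2 reactions are still seen in that class.

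The extreme case, with p and f both assumed:

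| p | f = 0.10 | f = 0.25 | f = 0.50 | f = 0.75 |
|---|---|---|---|---|
| 10% | 9% | 7.5% | 5% | 2.5% |
| 30% | 27% | 22.5% | 15% | 7.5% |

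If f = 0 there is no shift.

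**3. Exact intervals at a plausible group size.** SAP 2.4 gives 43 enrolled; over three safety groups that averages 43/3 = 14.3, taken as 15. Actual group sizes are not given. With an assumed 40% injection-site rate and Clopper-Pearson 95% intervals:

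| Unscreened | Whole group | Screened only | Unscreened counted as events |
|---|---|---|---|
| 5 of 15 | 4/15 = 26.7% (7.8–55.1) | 4/10 = 40.0% (12.2–73.8) | (4+5)/15 = 60.0% (32.3–83.7) |
| 10 of 15 | 2/15 = 13.3% (1.7–40.5) | 2/5 = 40.0% (5.3–85.3) | (2+10)/15 = 80.0% (51.9–95.7) |

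With no allergic reaction seen, the exact upper limit is 1 − 0.025^(1/n): 21.8% for n = 15, 30.8% for n = 10 and 52.2% for n = 5.

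**The case against.** **The link to the symptom screen is not explicit.** No visible text says that outcomes 3.2.3 and 3.2.4 are ascertained only through the Vaccine Symptom Screen. Item 3l waives one form, not adverse-event reporting. Table 6.1-4 schedules medical history and clinical assessments at entry even for people who have had both doses. Protocol section 7.0, the rest of 6.3.8, CM #1 and the Analysis Implementation Plan cannot be seen. This stands, and it makes the bias conditional. It does not supply the missing rule: the SAP does not say that recalled reactions count.

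**There may be no late entrants.** SAP v2.0 modified a Retrospective Safety Set to admit people with both doses before entry. SAP v3.0, finalized after accrual closed, removed that set as no longer relevant. This may mean that few or none entered late. It is not conclusive, because late entry remains in the treatment row of 5.3, and 7.5 still counts people vaccinated before entry.

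**The figures are assumed.** This also stands. Neither the reaction rates nor the unscreened shares come from the documents.

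**Reporting by dose would change the outcome.** SAP 3.2 defines it per participant over the whole window. By-dose proportions can therefore only supplement it, and a denominator tied to one form must not discard reactions reported by other routes.

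**The consequence is limited.** The outcomes are secondary and descriptive. SAP 7.5 already reports days from first vaccine to entry, which tells a reader part of what is needed.

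**Conclusion.** The gap is real and minor. The stated denominator includes people for whom the protocol may hold no systematic record of reactions, and neither the missing-data rule nor the worst-case analysis covers them. If there are such people and no other source captures their reactions, the two proportions and their exact limits are too low in the active-therapy and placebo groups. The direction follows from the text. The size is unknown and may be zero; p(1 − f) marks the largest expected loss.

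A reader might infer three stronger things, none of which the documents support:

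- That the reported rates are in fact biased. The number of late entrants is not given, and other routes of capture cannot be ruled out. The percentages above illustrate the mechanism and are not an effect size.
- That a test against naive participants is invalid. No formal contrast is planned; the groups are described side by side.
- That serious events go uncounted. Grade 3 or higher events, serious events and events that change vaccine receipt form a separate outcome running to Day 140, and this point makes no claim about it.

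**What to change.** In SAP 5.3 and 7.9, for outcomes 3.2.3 and 3.2.4 only:

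1. Keep the per-participant definition. Use as the main denominator the participants ascertained for every dose they received by Day 56, and state which sources count as ascertainment, including entry history if it is used.
2. Report the number not ascertained in each group.
3. Show the full Safety Set result alongside, counting any reaction captured by other routes.
4. Extend the existing worst-case analysis to unscreened participants. This matters because the ascertained denominator assumes that entry time is unrelated to reaction risk.
5. Optionally, add proportions after dose 1 and after dose 2 among those screened for each.
6. Make the *post-entry* wording in 7.6 consistent with the from-first-dose window in 5.3 and 7.9.

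If nobody entered more than 14 days after a dose, say so in 5.3. No re-tabulation is then needed, only the wording change in 7.6.

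The cost is small. Days from each dose to entry are needed. SAP 7.5 lists only the first dose, but vaccination is documented at entry (Table 6.1-4), so the dose 2 date should be on file. Smaller denominators widen the intervals, and the worst-case bounds may be too wide to say much. SAP 1.2 states that the final report was run under v3.0, so any new table should be labelled post hoc.

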~~For participants receiving community provided vaccine, screening evaluations to determine eligibility must be completed within 14 days prior to study entry unless otherwise specified.~~

- The first and second paragraphs of section 6.2.2, Entry Evaluations have been changed as follows.

For **all** participants ~~receiving study provided vaccine~~, entry evaluations must occur **≤28** days after screening evaluations unless otherwise specified.

~~For participants receiving community provided vaccine, entry evaluations must occur **≤14** days after screening evaluations unless otherwise specified.~~

8. Section 7.4 Study Monitoring. The second sentence of the third paragraph was revised as follows.

The first interim review will occur when 10 participants have enrolled to one select therapy group, **received their first dose of vaccine after study entry**, and their data through study Day 7 (7 days after the first vaccine dose) are available, or 3 months after the first

participant enrolls, whichever occurs first.

9. Section 10.0 Statistical Considerations was revised as follows.

- a. Section 10.2.1.1 (Primary Outcome Measure)
“Neutralizing antibody (NAb) level at least **140** days after the first dose of the study- or community-provided vaccine.”
- b. Section 10.2.2.2 (Secondary Outcome Measure)
“New Grade 3 or higher AE, or SAE, or AE leading to change or discontinuation in vaccine receipt from first dose of the mRNA-based COVID-19 vaccine and through **140** days after the first dose of vaccine.”
- c. Section 10.2.2.6 (Secondary Outcome Measure)
“Flow cytometry of PBMC for markers of exhaustion on B and T cells at study entry/Day 0, 56 **and 140** days after the first vaccine dose.”
- d. Section 10.4 Sample Size. The first sentence of the third paragraph was revised.

For the primary outcome measure of NAb levels **56 140** days after the first vaccine dose, we will calculate the ratio of geometric mean responses (GMRs) for participants with prior select investigational therapy exposure versus participants who received placebo.

e. Section 10.6 Analyses.

I. The first sentence of the fifth paragraph was revised.

The primary analysis population will include all participants who received at least one vaccine dose and provided NAb responses at least **56 140** days after the first vaccine dose.

II. The first sentence of the sixth paragraph was revised.

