7.6 Adverse Events

- Summary of post-entry reportable adverse events (per section 7.0 of study protocol)
- Listing of all adverse events by participant (public participant identifier)
- Summary of post-entry grade 3 or higher AE, SAE, or AE leading to a change or discontinuation in vaccine receipt from first dose of the mRNA-based COVID-19 vaccine through 140 days after the first vaccine dose

- Summary of post-entry grade 1 or higher allergic reactions from first dose of the mRNA-based COVID-19 vaccine through 56 days after the first vaccine dose
- Summary of post-entry grade 2 or higher infection site reactions from first dose of the mRNA-based COVID-19 vaccine through 56 days after the first vaccine dose

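### The 140-day safety outcome has three components, but SAP 5.3 and 7.9 estimate only one of them (Grade 3 or higher adverse events)

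*SAP*

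**What the plan says.** Three places define the outcome, and all include the same three components joined by an or:

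- Protocol Letter of Amendment #1, revised Section 10.2.2.2: "New Grade 3 or higher AE, or SAE, or AE leading to change or discontinuation in vaccine receipt from first dose", running through 140 days.
- SAP 3.2.2: "New Grade 3 or higher AE, or SAE, or AE leading to change or discontinuation in vaccine receipt".
- SAP 5.3, Outcome measures cell: "New Grade 3 or higher AE, SAE, or AE leading to change or discontinuation in vaccine receipt".

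Three places say what will be estimated or reported, and all name a single component:

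- SAP 5.3, Population-level summary measure: "Probability of having at least one Grade 3 or higher adverse event following first dose of vaccine through 140 days".
- SAP 5.3, Analysis approach: "Proportion of participants with at least one Grade 3 or higher adverse event through 140 days after the first vaccine dose", with an exact 95% confidence interval.
- SAP 7.9: "Probability of having at least one Grade 3 or higher adverse event through 140 days after the first vaccine dose".

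SAP 7.6 brings all three components into the report, as a "Summary of post-entry grade 3 or higher AE, SAE, or AE leading to a change or discontinuation in vaccine receipt". It covers post-entry events only and specifies neither a proportion nor a confidence interval.

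**The concern.** An estimand's summary measure and estimator should act on its own outcome variable. Here the outcome cell holds a composite, and the cells that turn it into a number hold one component. A programmer who follows the analysis cell would not count a participant who stopped vaccination for a Grade 2 event, or who had an SAE graded below 3, if nothing else qualified. A reader of the 5.3/7.9 result would nevertheless take it to be the 140-day secondary safety outcome.

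The table also disagrees with itself on missing data. The rule for participants who leave early says they "will have their outcome measures determined based on data available until the time of study discontinuation". For day 140 that outcome measure is the composite, while the analysis line beside it uses the narrower event.

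**Working it through.** The documents state no safety rate to reproduce, so the main check is a comparison of texts.

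| Place | Function | 140-day event |
|---|---|---|
| Protocol 10.2.2.2 (LOA #1) | definition | three components |
| SAP 3.2.2 | definition | three components |
| SAP 5.3 Outcome measures | definition | three components |
| SAP 5.3 Summary measure | quantity estimated | Grade 3+ only |
| SAP 5.3 Analysis approach | estimator, exact CI | Grade 3+ only |
| SAP 7.9 | report of the estimand | Grade 3+ only |
| SAP 7.6 | AE summary | three components, post-entry, no CI |

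**Are the two events equivalent?** Not by definition. The components are joined by an or, so each can qualify alone. SAP 5.3 itself lists stopping after the first dose for safety reasons as an intercurrent event handled by treatment policy. A participant who stops for a Grade 2 event and has no other qualifying event is a case under SAP 3.2.2 and a non-case under the analysis cell.

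**Direction.** Leaving out two components can only lower the proportion. The two figures agree if every participant with an SAE or vaccine-changing AE also had a new Grade 3 or higher AE. The estimator also drops the restriction to new events. Read literally, that could add participants, so that word needs restoring too.

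**Possible size.** The only documented number is 43 enrolled in total (SAP 2.4), which caps any safety group. Group sizes of 10 and 14 (43/3 = 14.3) and the event counts below are assumptions. Exact (Clopper-Pearson) 95% limits:

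- 0 of n: lower limit 0; upper limit 1 − 0.025^(1/n).
- 1 of n: lower limit 1 − 0.975^(1/n); upper limit is the 0.975 quantile of Beta(2, n − 1).

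For n = 14, the upper limit at 0 events is 1 − 0.025^(1/14) = 0.232, and the lower limit at 1 event is 1 − 0.975^(1/14) = 0.0018.

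| n | 0 events (Grade 3+ only) | 1 event (composite) | Shift in estimate | Shift in upper limit |
|---|---|---|---|---|
| 10 (assumed) | 0% (0 to 30.8) | 10.0% (0.3 to 44.5) | 10.0 points | 44.5 − 30.8 = 13.7 |
| 14 (assumed) | 0% (0 to 23.2) | 7.1% (0.2 to 33.9) | 7.1 points | 33.9 − 23.2 = 10.7 |
| 43 (ceiling) | 0% (0 to 8.2) | 2.3% (0.1 to 12.3) | 2.3 points | 12.3 − 8.2 = 4.1 |

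**The case against.** The best counter-argument is that the narrower phrase is shorthand. The 5.3 table abbreviates elsewhere: its Variable cell speaks only of an adverse event, with no grade. The three analysis lines follow the three outcome measures in order. SAP 7.9 ties its early-discontinuation sensitivity analysis to each outcome measure, and the version 3.0 change list records no narrowing. This is possible, but no text says so. The allergic-reaction and injection-site outcomes keep the same event and grade from the outcome cell through the analysis cells and into 7.9; only the composite is cut. SAP 7.6 shows that the authors wrote out all three components when they meant them.

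The second argument is that SAP 7.6 already reports the composite, so nothing is hidden. That stands in part: the events would appear in the report. But 7.6 is limited to post-entry events, whereas the outcome runs from the first dose and Cohort 1b participants may enter after one or both doses. It also specifies no exact interval and is not tied to the three safety groups of 5.3. The general grouping rule at the head of SAP 7 does not name the group without prior COVID-19. That is minor support only, because the same rule governs 7.9.

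Two limits stand in full. The Analysis Implementation Plan, which holds the table and coding detail, is not among the documents and may specify the composite. The outcome is secondary, exploratory and descriptive.

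**Conclusion.** The SAP is wrong as written: the proportion and exact interval it specifies need not be for the 140-day outcome it defines. The textual mismatch is certain. Its numerical effect is unknown, because the documents give no event counts or safety-group sizes, and it may be zero. If one participant qualified only through an omitted component and no one else had an event, the estimate would shift by 2.3 points at the ceiling of 43, or by 10 points in an assumed group of 10. No hypothesis test or error rate is involved. The correction should be made because groups this small make a single uncounted participant visible, and because the reported secondary outcome should be the one defined.

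**What to change.** Change three places: the SAP 5.3 summary measure, the SAP 5.3 analysis approach and SAP 7.9. In each, state the event as at least one of (a) a new AE of Grade 3 or above, (b) an SAE, or (c) an AE that led to vaccine receipt being changed or stopped, counted from the first dose to day 140. Give the proportion and exact 95% interval for each of the three 5.3 safety groups. State that the 140-day sensitivity analyses use this composite; 7.9 already implies this for early discontinuation. Keep Grade 3 or higher alone as a reported component.

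If the sponsor did intend the narrower event, SAP 3.2.2, the 5.3 outcome cell and Protocol 10.2.2.2 would have to change instead. That is the weaker course, since SAP 1.2 says the final analysis report was conducted under version 3.0.

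The cost is three wording edits and one table row per safety group. For the completed report, first check which event was tabulated, and re-run only if it was Grade 3 or higher alone.
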